### Exclusion criteria:

- Patients deemed to have poor prognosis, or patients to receive palliative treatment only (as advised by the Clinical Oncology team).
- Patients with less than 6 teeth before the radiotherapy start date.
- Patients with recurrent head and neck cancer, or patients receiving a repeat course of head and neck radiotherapy.
- Patients with diseases affecting tooth development (e.g. amelogenesis or dentinogenesis imperfecta) or salivary gland function (e.g. Sjogren's Syndrome).
- Patients with pre-existing trismus (mouth opening less than 35mm).

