Patients will be asked to refrain from smoking, eating and drinking, and other forms of oral stimulation (e.g. oral hygiene) 90 minutes prior to the collection of saliva. It is anticipated that the length of each patient's pre-radiotherapy dental assessment will be at least 90 minutes (based on current clinical practice). Patients will therefore be instructed not to engage in oral stimulation for 90 minutes after they have signed the written consent form at the start of the appointment.

-Ruler measurement of **mouth opening**. Maximum interincisal distance will be measured when the upper and lower central incisors are present (natural or prosthetic). Alternatively, the alveolar ridge(s) will be used as a reference point for measurement where no natural or prosthetic central incisors are present.

All of the above data, including the Oral Health Assessment Forms, will be recorded and stored in patients' clinical records (dental notes).

**-Oral hygiene practice and dietary assessments** will be performed using the World Health Organization's Oral Health Questionnaire for Adults.

**-Quality of life** and experience of **xerostomia** will be assessed using questionnaire booklets containing the European Organization for Research and Treatment of Cancer (EORTC) QLQC30 quality-of-life instrument, the associated head and neck specific module HN35, the Oral Health Impact Profile, and the modified Xerostomia Questionnaire.

**-Micro-costings study.** Patients will also be asked to complete a short questionnaire enquiring of their gross annual income, the mode of transport they used for attending their dental appointment, and whether another person accompanied them to their dental appointment. The micro-costings study questionnaire will be attached to the oral hygiene/diet/quality of life/xerostomia questionnaire booklet outlined above.

The questionnaire booklets will be completed anonymously. Upon acceptance into the study, a random number generator will assign each recruited patient a 6-digit anonymous code. Each patient will be informed of his or her anonymous code. This will be the only identifier recorded on completed questionnaire booklets.

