#### **1. Extractions**

The following table is intended to guide the decision-making process for pre-radiotherapy dental extractions in line with current practice. The decision to undertake extractions should be taken after careful consideration of individual tooth prognosis, tooth abutment potential, and the patient's medical history (see also 'SPECIAL CASES' below).

	Molars	Premolars	Anteriors
Apical disease	YES	YES when both marginal ridges lost	YES if post-crown
Furcation disease	YES	YES	N/A
Grade II mobile or worse	YES	YES	YES
Loss of >50% marginal bone loss	YES	YES	YES
Crown with secondary caries	YES	YES if post-crown	YES if post-crown
Crown with subgingival margins	YES	YES	NO
Caries or toothwear with suspected pulpal involvement	YES	YES when both marginal ridges lost	NO
Previous RCT/non-vital tooth	YES	YES when both marginal ridges lost	NO
Caries/tooth margin >1mm subgingival	YES	YES	YES
Root caries >1 surface	YES	YES	YES
Root perforation/ resorption/ fracture/ retained instrument	YES	YES	YES
Periodontal pocket >5mm	YES	YES	YES

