## **Protocol for post radiotherapy dental assessments**

Participants will be followed-up at 6 months, 12 months, and 24 months post-radiotherapy.

Patients will undergo dental assessment on a Wednesday morning or afternoon in the Prosthetics Department of the School of Dentistry, Belfast. The following measurements will be collected (using the same methods and examiners outlined above): charting of dental caries, 6-point clinical attachment loss and probing pocket depth charting, stimulated salivary flow rate, mouth opening, oral hygiene practice, dietary assessment, quality of life, patient reported xerostomia, micro-costings study.

N.B. – For each patient, all efforts must be made to ensure that saliva collection is undertaken at a similar time of day for each of the four dental assessment appointments (i.e. the pre-radiotherapy assessment appointment and the three post-radiotherapy assessment appointments). This is due to the diurnal variation in saliva production. Patients will be asked to refrain from smoking, eating and drinking, and other forms of oral stimulation (e.g. oral hygiene) 90 minutes prior to the collection of saliva at post-radiotherapy assessment appointments. These instructions will be explained and provided in writing, and attached with the post-radiotherapy assessment appointment letter as a reminder to patients.

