Secondary outcomes to be analysed include: quality of life, salivary flow rate, diet, oral hygiene practice, mouth opening, xerostomia (all change from baseline); tooth loss, and denture wear. Dichotomous outcomes will be analysed using chi-square tests and logistic regression as above. Continuous outcomes will be analysed as above, apart from variables with baseline measurements, for which ANCOVA will be used to compare outcome measurements adjusting for baseline. Adjusted analyses will use multiple linear regression models as above but with baseline measurements as an additional explanatory variable.

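### Mouth opening is read from the incisors or from the ridge according to what is present at each visit, so a patient whose landmark switches has a change from baseline that mixes jaw movement with tooth height.

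*Combined protocol and SAP*

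**What the plan says.** All references are to the combined protocol and SAP.

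- **Measurement rule (Clinical assessment).** "Maximum interincisal distance will be measured when the upper and lower central incisors are present (natural or prosthetic"; then "Alternatively, the alveolar ridge(s) will be used as a reference point for measurement where no natural or prosthetic central incisors are present". The bracketed plural allows one arch or both to be read from the ridge.
- **Follow-up (Protocol for post radiotherapy dental assessments).** Mouth opening is measured again at 6, 12 and 24 months "using the same methods and examiners outlined above".
- **Analysis (Statistical analysis).** The secondary outcomes are "quality of life, salivary flow rate, diet, oral hygiene practice, mouth opening, xerostomia (all change from baseline); tooth loss, and denture wear". For continuous variables with a baseline value, "ANCOVA will be used to compare outcome measurements adjusting for baseline". Mouth opening is also a listed potential confounder in the adjusted models for both primary outcomes, with no visit named.
- **Eligibility (Exclusion criteria).** The list includes "Patients with pre-existing trismus (mouth opening less than 35mm", with no landmark given.
- **Tooth loss after the baseline reading.** Extractions before radiotherapy follow from the treatment plan made at the baseline assessment. The table in section 1, Extractions, has a column for anterior teeth, and the special cases add teeth close to an oral tumour and possible full clearance. Extractions after radiotherapy are recommended only for teeth judged unrestorable.
- **Recording (Spreadsheets).** The clinical data sheets hold mouth opening; no field for the landmark is listed.

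**The concern.** A change score is meaningful only if both readings share the same reference points. Here the reference depends on the state of the mouth on the day, and the plan's own pathway can alter that state between baseline and follow-up. Tooth loss and denture wear are themselves secondary outcomes, so the plan expects both to vary.

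When the landmark switches, the ruler reading moves by the height between incisal edge and ridge even if the jaw opens exactly as before. Baseline adjustment does not remove this. For a patient read from the incisors at baseline, the baseline value carries no trace of the later switch, and no model term identifies it.

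At stake is whether mean change in mouth opening, and its association with radiation dose, describes jaw function or partly describes dentition. A smaller issue is that the 35 mm entry criterion may be applied to readings on two scales.

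**Working it through.** The plan states no figure on this point, so there is nothing to reproduce. The check is the wording, simple geometry and an illustration.

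**1. Can a patient switch under the rule as written?** Yes. The baseline reading comes before the extractions. In the 12 rows of the extraction table, the column for anterior teeth has 6 unconditional YES entries, 2 that apply only to post-crowned teeth, 3 NO and 1 not applicable. Later extractions and changes in denture wear are also possible. No section requires the baseline landmark to be kept, the landmark to be recorded, or a switched reading to be converted.

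**2. Effect on one patient.** Let h be the incisal-edge-to-ridge height in the arch that switches.

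- Incisor at baseline, ridge at follow-up: recorded change = true change + h (apparent gain).
- Ridge at baseline, prosthetic incisor at follow-up: recorded change = true change − h (apparent loss).
- Incisor lost, but a prosthetic incisor worn at the visit: no switch to the ridge.
- If both arches switch, h is replaced by the sum of the two heights.

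For example, with h = 8 mm (assumed), a true loss of 8 mm in a patient of the first kind is recorded as −8 + 8 = 0 mm.

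**3. Effect on the mean.** Mean shift = (share switching incisor to ridge − share switching ridge to incisor) × h.

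The documents give neither h nor the shares. Assume h = 5 to 11 mm per arch, 10 to 20% switching one arch from incisor to ridge, and none the other way:

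| Share switching | h = 5 mm | h = 11 mm |
|---|---|---|
| 10% | 0.10 × 5 = 0.5 mm | 0.10 × 11 = 1.1 mm |
| 20% | 0.20 × 5 = 1.0 mm | 0.20 × 11 = 2.2 mm |

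The same shares switching the opposite way would give −0.5 to −2.2 mm. Equal shares in both directions would leave the mean unshifted and only add noise.

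**4. Effect on a comparison of dose groups.** Spurious difference = (net share in one group − net share in the other) × h. It is zero if the net shares are equal. The documents give no switching rate by dose, so neither its size nor its sign can be stated.

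**5. Entry criterion.** A one-arch ridge reading of 35 mm corresponds to an incisor-equivalent opening of 35 − h, that is 35 − 11 = 24 mm to 35 − 5 = 30 mm under the same assumption. Entry requires at least six teeth, not central incisors, so such patients can present at baseline.

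**The case against.** The strongest reply is that the problem is small and partly covered.

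- **Prosthetic incisors count as present.** A patient whose lost incisors are replaced, and who wears the replacement at the visit, stays on the interincisal reference. This stands and narrows the problem to unreplaced or unworn teeth and to prostheses added after a ridge baseline.
- **Central incisors may seldom be lost.** The anterior column of the extraction table has several NO entries and covers all anterior teeth, and extractions after radiotherapy are restricted. This stands as to frequency: the documents give no rate.
- **Switches can be partly reconstructed.** Teeth are charted at every visit with codes for missing teeth. This stands for natural teeth. Charting does not show whether a prosthesis was in place during the reading, and the edge-to-ridge height cannot be measured once the teeth are gone.

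A reader might also infer more than the documents support:

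- *That the rule systematically hides trismus.* The error runs both ways, and 35 mm is only an entry criterion; follow-up analyses mouth opening as a continuous measure, not trismus as an endpoint.
- *That it biases the dose association in a known direction.* This needs switching to be linked to dose. More incisor loss in oral tumours with high tooth dose is plausible but not documented, and the documents offer no link to dose to the spared parotid gland, the exposure that leads the analysis.
- *That it undermines the primary outcomes.* Mouth opening enters those models only as a potential confounder. If the baseline value is used, later switching does not touch it; only differences of scale between patients remain.

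**Conclusion.** The point holds as a measurement defect of limited reach. Followed as written, the plan gives a wrong change in mouth opening for any patient who moves between incisor and ridge, and it provides no means to identify or correct this reliably. That conclusion rests on the wording and on geometry alone.

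The size does not. The illustrative shift of about 0.5 to 2.2 mm depends on assumed heights and one-way, one-arch switching rates. The documents give no standard deviation or target difference for mouth opening against which to judge it. One of eight secondary outcomes is affected directly. The change is worth making because it is cheap and because the height needed for correction is lost if it is not taken before extraction.

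**What to change.** 1. **Clinical assessment and post-radiotherapy assessments.** At every visit record the reference used in each arch (natural incisor, prosthetic incisor or ridge) and whether a prosthesis was worn for the reading. Add this to the four clinical data spreadsheets.
2. **Baseline.** Where central incisors are present, take one ruler reading from incisal edge to ridge in each arch, before any extraction.
3. **Statistical analysis.** Analyse change on same-reference values. Where the landmark has moved from incisor to ridge, subtract the recorded height for that arch to return to the baseline reference. Report how many patients were converted, and add a sensitivity analysis limited to patients whose landmark never changed.
4. **Patients with no central incisors at baseline.** Keep the ridge as the reference throughout, with any prosthesis out for the reading. No conversion height exists for natural incisors already lost, so flag that these readings are not on the same scale as the 35 mm entry criterion. The Exclusion criteria and Clinical assessment sections must be reconciled on this.

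Cost: one or two extra ruler readings at baseline and one extra data field per visit, with an entry for each arch. The converted values carry a small error from ridge resorption after extraction; the sensitivity analysis shows whether conclusions depend on them.

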#### Radiographs

The decision to prescribe, take, and interpret dental radiographs for the purposes of diagnosis and treatment-planning should be made on a case-by-case basis and follow current clinical practice. There should be clear justification for the medical exposure of patients in line with the Ionising Radiation (Medical Exposure) (Amendment) Regulations (Northern Ireland) 2010. The following criteria, adapted from the FGDP's Selection Criteria for Dental Radiography, is intended to guide the decision-making process:

#### **Dental pantomogram (DPT) - mandatory**

IOPAs – symptomatic teeth, clinical signs (sinus, swelling), caries with suspected pulpal involvement, toothwear with suspected pulpal involvement, previous root canal treatment (RCT), crowned teeth, heavily restored teeth with restoration in close proximity to pulp, clinical attachment loss >6mm, furcation disease.

Bitewings – lack of clarity regarding the presence of interproximal caries on DPT.

Radiographic evidence of secondary caries or caries into dentine will be recorded on each patient's Oral Health Assessment Form.

#### Other special investigations

Electric pulp test – caries with suspected pulpal involvement, toothwear with suspected pulpal involvement, heavily restored teeth with restoration in close proximity to pulp.

## **Prevention and treatment planning**

All patients will receive standardised oral hygiene and dietary advice:

### Diet advice

- Sugary and acidic food/drink to be consumed at mealtimes only
- Rinse mouth with 0.05% fluoride mouthwash after each sugar attack
- Advice on the use of sugar-free medications

### Oral hygiene instructions

- Powered or manual medium toothbrush to be used (Bass technique)
- 5,000ppm Duraphat fluoride toothpaste to be used twice daily
- 0.05% fluoride mouthwash to be used at least once daily (different time from brushing)
- Floss and/or interdental brushes (as appropriate) to be used daily
- Corsodyl (chlorhexidine gluconate) 0.2% mouthwash to be used twice daily for 1 week prior to radiotherapy

### Denture hygiene instruction

- Don't wear dentures during the course of radiotherapy if possible
- Rinse dentures after every meal in cold running water
- Clean dentures at least once daily with a toothbrush and 5,000 ppm Duraphat fluoride toothpaste
- Soak in Milton's (1 in 80 dilution) overnight if the denture is made of plastic only
- Alternatively, soak in Corsodyl (chlorhexidine gluconate) 0.2% overnight if the denture has metal components

A dental treatment plan will be formulated for each patient to ensure adequate dental fitness prior to radiotherapy. Consultants in Restorative Dentistry, will oversee patients' treatment plans. Dental treatment required pre-radiotherapy (e.g. restorations and extractions) will be co-ordinated by the School of Dentistry in line with current practice, including the possibility of routine treatment within the primary care setting (i.e. completed by the patient's general dental practitioner).

To facilitate the micro-costings study, all patients will be asked to retain details of any treatment costs that they incurred from their general dental practice. Patients will be asked to provide this cost information at follow-up appointments (for example, with the production of invoices). Information on the cost of dental treatment incurred will be recorded on each patient's anonymised questionnaire booklet completed at the subsequent follow-up appointment.

### **Treatment planning components:**

May include any combination of the following:

#### **1. Extractions**

The following table is intended to guide the decision-making process for pre-radiotherapy dental extractions in line with current practice. The decision to undertake extractions should be taken after careful consideration of individual tooth prognosis, tooth abutment potential, and the patient's medical history (see also 'SPECIAL CASES' below).

	Molars	Premolars	Anteriors
Apical disease	YES	YES when both marginal ridges lost	YES if post-crown
Furcation disease	YES	YES	N/A
Grade II mobile or worse	YES	YES	YES
Loss of >50% marginal bone loss	YES	YES	YES
Crown with secondary caries	YES	YES if post-crown	YES if post-crown
Crown with subgingival margins	YES	YES	NO
Caries or toothwear with suspected pulpal involvement	YES	YES when both marginal ridges lost	NO
Previous RCT/non-vital tooth	YES	YES when both marginal ridges lost	NO
Caries/tooth margin >1mm subgingival	YES	YES	YES
Root caries >1 surface	YES	YES	YES
Root perforation/ resorption/ fracture/ retained instrument	YES	YES	YES
Periodontal pocket >5mm	YES	YES	YES

#### **SPECIAL CASES**

Dental phobic patients – may consider additional extraction of any tooth with caries.

Impacted/unerupted teeth – extract when in communication with oral cavity, carious, or other pathology suspected (e.g. cyst formation, resorption of adjacent teeth).

Retained roots/apices – leave when no pathology and encased entirely within bone.

Patients deemed to have poor prognosis or to receive palliative treatment only – may limit number of extractions on this basis.

Dental neglect (toothbrushing <1x per day, intake of >5 sugar attacks per day, caries affecting >75% of remaining teeth) – may consider additional extraction of teeth or complete dental clearance.

Patients with oral cancer – additional teeth in close proximity to tumour may require removal as part of the oncology surgical approach.

Patients taking bisphosphonate medications – need to liaise with Oral Surgery or Maxillofacial Team.

## 2. Dental restorations (“fillings”)

**Permanent restorations should be undertaken where possible.**

**Minimum** = Render tooth caries-free (including crown removal where appropriate) and adequate temporization (e.g. with glass ionomer restoration).

**Minimum when a tooth has been diagnosed with pulpal/apical pathology** = 1st stage RCT and adequate temporization (e.g. with glass ionomer restoration).

## 3. Non-surgical periodontal treatment

Non-surgical periodontal treatment to remove supra and subgingival calculus and plaque.

## **Protocol for post radiotherapy dental assessments**

Participants will be followed-up at 6 months, 12 months, and 24 months post-radiotherapy.

Patients will undergo dental assessment on a Wednesday morning or afternoon in the Prosthetics Department of the School of Dentistry, Belfast. The following measurements will be collected (using the same methods and examiners outlined above): charting of dental caries, 6-point clinical attachment loss and probing pocket depth charting, stimulated salivary flow rate, mouth opening, oral hygiene practice, dietary assessment, quality of life, patient reported xerostomia, micro-costings study.

N.B. – For each patient, all efforts must be made to ensure that saliva collection is undertaken at a similar time of day for each of the four dental assessment appointments (i.e. the pre-radiotherapy assessment appointment and the three post-radiotherapy assessment appointments). This is due to the diurnal variation in saliva production. Patients will be asked to refrain from smoking, eating and drinking, and other forms of oral stimulation (e.g. oral hygiene) 90 minutes prior to the collection of saliva at post-radiotherapy assessment appointments. These instructions will be explained and provided in writing, and attached with the post-radiotherapy assessment appointment letter as a reminder to patients.

### Radiographs

The decision to prescribe, take, and interpret dental radiographs for the purposes of diagnosis and treatment-planning should be made on a case-by-case basis and follow current clinical practice. There should be clear justification for the medical exposure of patients in line with the Ionising Radiation (Medical Exposure) (Amendment) Regulations (Northern Ireland) 2010. The following criteria, adapted from the FGDP's Selection Criteria for Dental Radiography, is intended to guide the decision-making process:

DPT – suspected bony pathology (e.g. osteoradionecrosis, cyst), gross caries or periodontal disease assessment, wisdom tooth assessment.

IOPAs - symptomatic teeth, clinical signs (sinus, swelling), caries with suspected pulpal involvement, toothwear with suspected pulpal involvement, previous RCT, crowned teeth, heavily restored teeth with restoration in close proximity to pulp, clinical attachment loss >6mm, furcation disease.

Bitewings – where visualization of approximal surfaces of posterior teeth impeded.

Radiographic evidence of secondary caries or caries into dentine will be recorded on each patient's Oral Health Assessment Form as above.

#### Other special investigations

Electric pulp test – caries with suspected pulpal involvement, toothwear with suspected pulpal involvement, heavily restored teeth with restoration in close proximity to pulp.

Patients' general dental practitioners will also be asked to immediately inform the research team if they carry out any dental treatment during the course of the study.

